6.0 Microbiological analyses

6.1 Salivary test

In an epidemiological study with repeated tests, a simple and non-invasive method to test participants is mandatory. The salivary sample collection is simple, painless and can be performed by the participant himself (under supervision for younger participants). A salivary collection device is developed by the University of Liège (Belgium) and currently used by university students of ULiège.

For this study a saline mouth rinse/gargle sample will be used to collect the saliva from participants. This self-collected sampling was tested on 50 participants, aged 4 to 71 years and showed a sensitivity of 98% to detect SARS-CoV-2 by PCR compared with nasopharyngeal swab (19).

6.2. Real-time SARS-CoV-2 PCR

Saliva will be extracted using the MagMAX Viral/pathogen Nucleic Acid Isolation kit on a KingFisher automated platform (ThermoFisher). An unrelated MS-2 phage RNA sequence is added to each specimen to demonstrate the process efficiency. Purified RNA will then be retro-transcribed and amplified on a QuantStudio5 real-time PCR platform with the TaqPath™ COVID-19 RT-PCR kit (Thermo Fisher), which targets ORF1ab, N and S coding sequences using three different sets of primers and probes.

In case of a positive salivary PCR test for SARS-CoV-2 with a maximum Ct of 30, a whole-genome sequencing of the virus will be done at the medical microbiology facility (MBLG) of the UCLouvain (Brussels)

RNA is extracted from the specimen using the QIAamp viral RNA mini kit (QIAGEN). Fifty ng of purified RNA are then retro-transcribed using the Maxima H minus double-stranded cDNA synthesis kit (Thermo Scientific) following the manufacturer recommendations. A DNA NGS-library is then created using the Nextera DNA Flex for enrichment library kit (Illumina). Briefly, 50 to 1000 ng of cDNA are restricted in small fragments in order to create a DNA library of

approximately 300 nucleotides long using bead-linked transposomes (eBLT) (Illumina).

That tagmentation process is followed by a DNA clean-up and an amplification using unique-dual primers (IDT for Illumina UDI set of primers) recognizing the sequence added to each DNA strand during the tagmentation phase and adding a specific sequence to all strands of each sample. Amplified libraries are purified and dosed in spectrophotometry. Libraries are then pooled equimolarly and hybridized with a capture probe panel targeting SARS-CoV-2 as well as 40 other common respiratory viruses (Respiratory Virus Panel v2, Illumina). The enriched pooled library is finally amplified and purified. After a spectrophotometric dosage, the final library is diluted to 100 picomolar and charged on either an iSeq100 or NextSeq550 Mid-output cartridge allowing respectively 8 million or 260 million paired-end reads, in a 2 x 150 bp format. Each sample needs a minimum of 1 million reads to ensure a good coverage of the SARS-CoV-2 genome.

Raw sequences in a fastq format are processed through two different bioinformatic pipelines. First, the Dragen RNA pathogen analysis suite available through the BaseSpace Illumina online platform allows the generation of a consensus sequence and gives a percentage of each viral species detected in the library. Second, the Integrated Database Network System (IDNS) coupled to the advanced sequencing platform NGS pipeline from Smartgene allows the generation of SARS-CoV-2 consensus sequences and sequence comparisons in order to define sequence mutations in nucleotide or amino acid format. Phylogenetic analysis is available with a set of reference or personal sequences. Association of metadata to each sample allows selective analysis and group comparisons.

Whole-genome sequences will be shared on the GISAID open-source international platform. Clade determination and comparison to published SARS-CoV-2 sequences in a phylogenetic tree format is available through the NextClade web site.

6.3. SARS-CoV-2 serology

For Baseline seroprevalence data we will use a lateral flow test antibody IgG/IgM assay (colloidal gold) (Avioq) (Avioq, Bio-Tech, Shandong, China) CE-labelled. Sensitivity for Both IgM and IgG was 68.8% (IC 95% 60.3-76%) and the specificity was 95.8% (IC 95% 88.5-98.6%) (20).

7.0 Statistical analyses plan

7.1 Sample size and statistical analysis

As a pilot study, no formal sample size determination was performed. The expected number of children is 2400 (4 times 200 plus 4 times 400), the expected number of adult school attenders is 200, and the expected number of classes is 72. With an incidence around 0.5-1%, the expected number of cases is 120-240. Initial incidence and then secondary attack rates (as transmission estimator) will be calculated and compared between gender, across age, and between the three kinds of schools using Poisson or Binomial negative regression if overdispersion. Characteristics of classes will be compared between schools using ANOVA with F-tests for continuous variable and chi-square or Fisher exact tests for discrete variables. Any significant difference will be considered for correlation with incidence rates (per classes) and attack rates within the Poisson or Binomial negative regression. A cluster effect (Rho = 1.09 or ICC=0.09) will be assessed for weighting data analysis. Estimates will be presented with their 95% Confidence interval. Differences will be presented as absolute and relative differences.

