Endpoints	
 - Time varying number and proportion of children infected with SARS-CoV-2 secondary to an infected classmate (transmission rate inside school but from a child to a child). - Time varying number and proportion of adult school-attenders infected with SARS-CoV-2 secondary to an asymptomatic infected child (transmission rate inside school but from a child to an adult); - Time varying number and proportion of children infected with SARS-CoV-2 secondary to an infected adult school attender (transmission rate inside school but from an adult to a child);

	
 - Time varying number and proportion of children infected with SARS-CoV -2 secondary to a household contact or outside the school (transmission rate from outside school).
Statistical analyses plan	
Sample size determination
 
As a pilot study, no formal sample size calculation was performed. The expected number of children is 2400, the expected number of adult school attenders is 200, and the expected number of classes is 72.
 
Initial incidence and then secondary attack rates will be calculated and compared between gender, across age, and between the three kinds of schools using Poisson or Binomial negative regression if overdispersion. Analyses will be weighted to correct for cluster effect of classes (ICC=0.09).

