4.3 Selection of participating schools

All Belgian primary schools of the Federation Wallonie – Bruxelles that have organized a resumption of school activities with the social control measures recommended by the government, are eligible for the study. All children and school attenders attending included schools will be eligible to participate.

Each participating school will be considered as a statistical cluster because children within a school share more correlation together than with children from other schools (children are not an independent and identically distributed (i.i.d.) sample) and an intraclass coefficient (ICC) of 9% will be used in analysis.

We will enrol schools according to the following three criteria:

- School size: small school versus a large one

- Incidence of Sars-CoV-2 infection during the first wave of the pandemic in April 2020
 - Regions/cities with a low incidence (from 1.5 to 4.9 per thousand inhabitants on May 6th, 2020)
 - Regions/cities with a high incidence (from 5.0 to 7.5 per thousand inhabitants on May 6th, 2020)
- Socio-economic level of the school: low socio-economic level versus high level, based on ISE that is an official Belgian 20-point-scale index for all schools of the Federation Wallonie-Bruxelles (FWB).

Crossing those three criteria leads to eight categories of schools and one school of each category will be sampled

- Small school - very low incidence city - low socio-economic level
- Small school - very low incidence city - high socio-economic level
- Small school - very high incidence city - low socio-economic level
- Small school - very high incidence city - high socio-economic level
- Large school - very low incidence city - low socio-economic level
- Large school - very low incidence city - high socio-economic level
- Large school - very high incidence city - low socio-economic level
- Large school - very high incidence city - high socio-economic level

According to the definition of the FWB, investigators consider a small school a school with less than 300 children enrolled in the school and a large one a school with more than 300 children.

To determine regions with the highest and lowest incidence of SARS-CoV-2 infection during the first pandemic wave in Belgium investigators will refer to the epidemiological reports of Sciensano: <https://covid-19.sciensano.be/fr/covid-19-situation-epidemiologique>

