4.4.1 Inclusion criteria

- All children registered and attended the selected primary schools of the Fédération Wallonie - Bruxelles and adult's school attenders working in the same selected schools.
- Signed informed assent form by child and informed consent form by theirs parents (or legal guardian) and by adult's school attenders before enrolment

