5.1 Inclusion day

All participants, children and adults school attenders, will be tested at the inclusion day with

- a salivary SARS-CoV2 PCR test collected in the school, under investigators supervision
- a rapid serological test by finger prick (AVIOQ[®]) to determine the seroprevalence of SARS-CoV-2
- All participants (children and adult school attenders) will be invited to complete an electronic questionnaire when possible and a paperback questionnaire otherwise.

The questionnaire will address the following information (see attached file) partially inspired of the questionnaire used in the prevalence study *“Prevalence and incidence of antibodies against SARS-COV-2 in children measured for one year in Belgium: a sero-epidemiological prospective cohort study”* (study coordinator: [name], Sciensano).

- Socio-demographic data: gender, birth date, home postal code, a contact email address, a contact mobile number, country of birth of child and parents
- Housing information: number of people in the household, number of siblings, number of sleeping rooms, distance between school and home
- Exposition information: pre- and after-school daycare attending, extracurricular activities, parent's profession, transportation means between home and school

The salivary SARS-CoV2 sample will be performed at school by the participant him or herself under the supervision of the subinvestigators (80 medical students on contract) for minor

participants. An explanatory film on the method of self-performing the saliva sample will be provided to participants. The children and the teachers will use a garling method to produce saliva. The full procedure is explained in the explanatory film. The participant will wear an adapted mask while gargling. A full explanation of the used gargling sampling technic is also well detailed in the attached paper (19)

The procedure will be performed in a well-ventilated space one participant at a time. The medical student who will collect the sample will wear adapted personal protective equipment (PPE) in order to reduce the risk of transmission to as good as 0. The PPE will include FFP2 mask, gloves, glasses and a protective gown.

After collection, salivary samples will be transported to one of the three participating laboratories (UCLouvain - ULiège - ULB) by the medical student.

Teachers of each class will be invited to complete a questionnaire once with the following questions

- Number of children in the classroom

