- Size of the classroom
- Ventilation system and heating system of the classroom (CO2 sensor if any)
- Sanitary protocols of the school: eg hand washing recommendations
- Play-time space: indoor or outdoor
- Lunch space: in the classroom, school cafeteria, etc
- Organisation of pre- and after-school daycare attending: separation according to levels or mix of all classes. Number of children attending.

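### Class characteristics reach the per-class regression only through a between-school significance test that is unrelated to infection

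*Combined protocol and SAP*

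**What the plan says.** Section 7.1 first describes the main regression. Initial incidence and secondary attack rates are "compared between gender, across age, and between the three kinds of schools using Poisson or Binomial negative regression if overdispersion". Gender, age and kind of school thus enter directly; none of them is a characteristic of a class.

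Class characteristics are handled next, in two steps. First, "Characteristics of classes will be compared between schools using ANOVA with F-tests for continuous variable", with chi-square or Fisher exact tests for discrete items. Second, "Any significant difference will be considered for correlation with incidence rates (per classes) and attack rates within the Poisson or Binomial negative regression".

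The characteristics come from the teacher questionnaire in section 5.1. Its items include "Number of children in the classroom" and "Ventilation system and heating system of the classroom (CO2 sensor if any", and also room size, sanitary protocols, play and lunch space, and how daycare is organised. Section 5.1 gives no analysis rule for them. The statistical part of the synopsis (section 1.0) does not mention class characteristics; it repeats the gender, age and school comparison and adds: "Analyses will be weighted to correct for cluster effect of classes (ICC=0.09)".

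On the schools, section 4.3 says: "Crossing those three criteria leads to eight categories of schools and one school of each category will be sampled".

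**The concern.** The screen asks whether a factor is unevenly spread over schools. The regression asks whether the factor goes with infection. These are different questions, and the answer to the first decides which factors are put to the second.

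What is at stake depends on the purpose of the step, which the plan does not state:

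- **Class factors of interest in themselves.** A factor that varies from room to room but has a similar distribution in every school would usually be left out, although within-school variation is the kind that can be separated from school. A factor fixed by school would nearly always enter, although with one school per category it is largely confounded with school.
- **Adjustment of the school comparison.** Leaving out balanced factors does little harm. But confounders are then chosen by p-value, and with 72 classes a non-significant factor need not be a balanced one.

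The plan also names no list of class factors, so the content of the model is settled only once the data are in.

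**Working it through.** **Inputs from the documents.** Eight schools (section 4.3). Section 7.1 gives 2400 children, 72 classes and an ICC of 0.09. The child total reproduces: 4 × 200 + 4 × 400 = 2400.

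**Assumptions.** Six grades, with one class per grade in small schools and two in large ones, so that 4 × 6 + 4 × 12 = 72, matching the stated number of classes. The screen's level is not stated; 5% is used, in line with the 95% intervals. The factor is continuous and normal. The share s of its variance that lies between schools is not given for any item, so a range is shown.

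**1. Chance of passing the eight-school test.** With a balanced approximation of 9 classes per school, the critical value of F(7,64) is 2.156, and

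P(pass) = P[F(7,64) > 2.156 / (1 + 9s/(1 − s))].

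- s = 0: P[F > 2.156] = 0.05.
- s = 0.20: 1 + 9 × 0.20/0.80 = 3.25; 2.156/3.25 = 0.663; P = 0.70.
- s = 0.30: 1 + 9 × 0.30/0.70 = 4.86; 2.156/4.86 = 0.444; P = 0.87.

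Simulation with the unequal layout (40,000 runs per setting) gives:

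| Between-school share | 0% | 10% | 20% | 30% | 50% |
|---|---|---|---|---|---|
| Passes the eight-school test | 5% | 38% | 69% | 86% | 98% |

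Infection is not a variable in this test. A simulation that added infection confirmed the consequence: at a 30% share, a factor with no effect passed about 86% of the time and one with a rate ratio of 1.5 or 2.0 per SD passed 85 to 87%.

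**2. The other reading of the comparison.** If schools here means the three kinds of schools named one sentence earlier (size, incidence, socio-economic level), a factor qualifies when any of three two-group contrasts is significant. In the same layout this happens 14, 39, 58, 69 and 83% of the time at the same shares.

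**3. Imbalance left among factors not flagged.** Take two kinds of school with 36 classes each (by incidence or socio-economic level). Among factors that fail the eight-school test, at shares of 0 to 30%, the absolute difference in means, in within-school SD, has a median of 0.16 to 0.21 and a 90th percentile of 0.38 to 0.49.

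For scale, assume a rate ratio of 1.2 to 1.5 per SD of the factor. A difference of 0.2 SD shifts the comparison by a factor of 1.2^0.2 = 1.04 to 1.5^0.2 = 1.08. A difference of 0.49 SD shifts it by 1.2^0.49 = 1.09 to 1.5^0.49 = 1.22.

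**The case against.** The strongest case against raising this has four parts.

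- **Little depends on it.** Sections 3.1, 3.2 and 3.4 list no objective, outcome or endpoint on class factors, and section 7.1 calls the study a pilot. This stands, and it limits the point to an optional improvement.
- **Selecting covariates without looking at the outcome is a virtue.** It does avoid outcome-driven selection. A list fixed in advance avoids it equally well, without tying a factor's entry to its spread over schools.
- **Many items may pass.** Sanitary protocols and the organisation of daycare are worded as school matters, and a factor with a high between-school share passes nearly always. This stands too. The loss falls on items that vary mainly within schools, and the documents do not show which those are. The items that pass easily are also the hardest to separate from school.
- **Not adjusting is not necessarily bias.** Class size or ventilation may be part of how school size or socio-economic level acts. This is correct, so the shifts in the working are differences between unadjusted and adjusted comparisons, and count as bias only if the adjusted comparison is the target.

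A reader might also infer more than the documents support:

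- *That other class factors are barred.* Section 7.1 says significant differences will be considered; it does not expressly exclude the rest.
- *That an unflagged factor may realistically differ by 0.92 SD between kinds of school.* That is the algebraic limit, sqrt(7 × 2.156/18) = 0.916, reached only if all between-school difference lies on one contrast. In simulation the 99th percentile among unflagged factors is 0.58 to 0.70 SD.
- *That the kinds-of-school reading makes the screen far stricter.* This follows only from looking at a single contrast. The plan speaks of any significant difference, and the three contrasts together give the higher rates shown in the working.

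**Conclusion.** The point holds as an optional improvement to a secondary, exploratory analysis. The only stated route for class characteristics is a test that does not depend on their relation to infection. A factor with none of its variance between schools enters about 5% of the time, one with a 10% share about 38%, and one with a 50% share about 98%. If the step is for adjustment, the imbalance that goes unflagged is typically about 0.2 SD, with a 90th percentile of about 0.4 to 0.5 SD.

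These figures rest on the assumed layout of 6 or 12 classes per school, a 5% level, a normal factor, and a range of between-school shares that the documents do not supply. The fact that infection plays no part in the screen rests on none of them.

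A reader might infer that the transmission results are compromised. They are not: the number and proportion of infections by source, in section 3.4, do not pass through this step. Nor do the documents support saying that a real class effect would otherwise be found reliably, since no power is stated and the plan expects clustering of infection by class.

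**What to change.** In section 7.1, replace the significance filter with a short list of class factors chosen in advance from the teacher questionnaire, for example number of children, room size, ventilation, lunch place and daycare mixing. Then:

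- Fit each factor in the planned Poisson or negative binomial regression whatever its between-school p-value, allowing for school (for example a random intercept) and for class overdispersion.
- Use the log number of participants tested as offset for incidence, and the log number of exposed contacts for attack rates. Enrolled class size is not the right denominator, because entry requires "Signed informed assent form by child and informed consent form by theirs parents" or guardian, so only consenting pupils are tested.
- Report rate ratios with 95% confidence intervals, labelled exploratory.
- Flag factors that are constant within schools as confounded with school. This limit comes from the design and remains with or without the screen.
- Keep the between-school tests as a descriptive table, and state whether they compare the eight schools or the kinds of school.

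The cost is some SAP wording and a few more model fits on data already to be collected. The downside is wide intervals. With about 33.3 children per class and an ICC of 0.09, the design effect is 1 + 32.3 × 0.09 = 3.91. At the plan's own 120 to 240 cases, the 95% interval for a 1-SD difference is roughly the estimate divided and multiplied by exp(1.96 × sqrt(3.91/120)) = 1.42 to exp(1.96 × sqrt(3.91/240)) = 1.28, before any school-level variation, and wider with fewer cases. The school variance would be estimated from only eight schools.

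### The cluster effect is given as both 1.09 and 0.09, and the 0.09 is attached to classes in one place and to schools in another, so the planned confidence intervals are not defined

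*Combined protocol and SAP*

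**What the plan says.** Three places in the combined protocol and SAP describe the clustering.

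- Section 7.1: "A cluster effect (Rho = 1.09 or ICC=0.09) will be assessed for weighting data analysis". No level is named and no formula links the two numbers.
- Section 1.0 (Synopsis), statistical row: "Analyses will be weighted to correct for cluster effect of classes (ICC=0.09". The level here is the class, although the sampling row of the same Synopsis treats each school as a cluster.
- Section 4.3: each school is a statistical cluster "because children within a school share more correlation together than with children from other schools", and "an intraclass coefficient (ICC) of 9% will be used in analysis". The level here is the school.

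On the design, section 4.3 says: "Crossing those three criteria leads to eight categories of schools and one school of each category will be sampled". Section 7.1 gives the sizes: "The expected number of children is 2400 (4 times 200 plus 4 times 400" and "the expected number of classes is 72". It plans to compare rates "between the three kinds of schools using Poisson or Binomial negative regression if overdispersion", and promises 95% confidence intervals with absolute and relative differences.

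**The concern.** An analyst cannot carry out the weighting as written. One of the two numbers is impossible as a correlation and does not match the other at any cluster size in the plan. The level to which 0.09 belongs changes from section to section. Two competent analysts could both follow the text and report intervals of very different width.

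The level matters most for the school comparisons. Size, area incidence and socio-economic level vary only between the eight schools. A correction for classes alone treats classes of the same school as independent, yet section 4.3 gives within-school similarity as its reason for clustering. The intervals promised for rates and differences are what is at stake. No sample size depends on this, because none was calculated.

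**Working it through.** **Inputs.** From section 7.1: 2400 children, four schools of 200 and four of 400, 72 classes. ICC 0.09 from all three places. Class size is 2400/72 = 33.3 and mean school size is 2400/8 = 300. Assumed, because the documents give no value: the school ICC r, meaning the correlation between children of the same school in different classes.

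**Step 1: can 1.09 be reproduced?** Design effect = 1 + (m − 1) × 0.09.

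| m | Design effect |
|---|---|
| 2 | 1.09 |
| 33.3 (class) | 3.91 |
| 200 (small school) | 18.91 |
| 300 (mean school) | 27.91 |
| 400 (large school) | 36.91 |

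Only m = 2 gives 1.09, where the formula is simply 1 + 0.09. Other readings fail too: the square root of the class design effect is 1.98, 1/(1 − 0.09) = 1.099, and (1 + 0.09)/(1 − 0.09) = 1.198. A design effect of 1.09 at class size would need an ICC of 0.09/32.3 = 0.0028.

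**Step 2: how much does the level matter?** 27.91/3.91 = 7.1 in variance. With the size-weighted mean school size, (4 × 200² + 4 × 400²)/2400 = 333.3, the school value is 30.91 and the ratio is 7.9.

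**Step 3: what does the class reading leave out?** For the area-incidence or socio-economic contrast, each arm has two schools of 200 and two of 400, so the size-weighted m is again 333.3. If the within-class ICC is 0.09, the variance factor is 3.91 + (333.3 − 33.3) × r. The SE ratio is √(factor/3.91), and coverage of a nominal 95% interval is 2Φ(1.96/ratio) − 1.

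| Assumed r | Factor | SE ratio | Coverage |
|---|---|---|---|
| 0 | 3.91 | 1.00 | 95% |
| 0.005 | 5.41 | 1.18 | 90% |
| 0.01 | 6.91 | 1.33 | 86% |
| 0.02 | 9.91 | 1.59 | 78% |

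The size contrast (4 × 200 v 4 × 400) gives 95, 91, 88 and 81%. At an assumed 50% participation the area or socio-economic contrast also gives 95, 91, 88 and 81%. The overall rate has the same factor as the table when it is meant to describe more than these eight schools.

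**Step 4: does a negative binomial fit to class counts repair this?** Simulated layout: 72 classes of 33 in eight schools (four with 6 classes, four with 12), beta-binomial counts, total within-class ICC 0.09. Coverage for r = 0, 0.005, 0.01 and 0.02:

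- School contrast, assumed rates 1, 5 and 10% (1000 runs per cell; at the 1% rate, runs with no case in an arm were dropped): 94–95, 90–92, 84–89 and 74–79%.
- Overall rate, assumed rates 5 and 10% (400 runs per cell): about 95, 91, 86–90 and 78–81%.
- Four-v-four comparison of school rates with t on 6 df: 94–98% throughout.

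**Step 5: the other direction.** If 0.09 were imposed at school level while the class ICC was 0.09 and r was 0.01, the variance factor used would be 30.91 against 6.91. SEs would be √(30.91/6.91) = 2.1 times too large.

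These figures concern incidence. Secondary attack rates have contacts of index cases as denominators and are not quantified here.

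**The case against.** The best defence has four parts. The study is a pilot without a formal sample size. Section 7.1 says the cluster effect will be assessed, which may mean estimated from the data. Negative binomial regression on rates per class absorbs class-level overdispersion without an external ICC. Section 4.3 does name the school as a cluster, so school correlation has not been forgotten.

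Much of this stands. Pilot status excuses the missing sample size, and section 4.3 means the plan cannot be said to ignore schools. But section 4.3 also says the 9% will be used, which sits badly with estimation. The negative binomial model is conditional on overdispersion, the record unit is not fixed for every analysis, and that model does not link classes of the same school.

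A reader might go further in three ways that the documents do not support.

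- **That 1.09 will multiply the variance.** In a child-level fit at full participation with a class ICC of 0.09, SEs would be understated √(3.91/1.09) = 1.89-fold and coverage would be about 70%. The plan never says 1.09 is used this way, and its reference to incidence per class points elsewhere.
- **That all intervals will be too narrow.** This does not hold under the school reading (step 5), nor for within-class contrasts such as gender.
- **That a class-count model makes overall rates safe.** That holds at a school ICC of 0, or if only these eight schools are of interest. Otherwise overall rates lose about as much coverage as the school contrasts.

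**Conclusion.** The inconsistency is certain and needs no outside assumption: 1.09 is neither a correlation nor the design effect at any class or school size in the plan, and the same 9% is assigned to two levels whose implied variances differ about 7-fold. The direction of error is not fixed by the documents.

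The loss of coverage is conditional. It requires that the class reading is followed, that the within-class ICC is 0.09, and that some school-level correlation exists. Coverage is then about 95, 90, 86 or 78% for an assumed school ICC of 0, 0.005, 0.01 or 0.02, for the school-factor comparisons and for overall rates generalised beyond the eight schools. At a school ICC of 0 nothing is lost. The three kinds of schools in section 7.1 are read here as the three binary criteria of section 4.3, which is an interpretation. This should be fixed before analysis.

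**What to change.** - Delete Rho = 1.09. If a planning design effect is quoted, write it as 1 + (m − 1) × ICC, with the level and m stated.
- Reconcile the Synopsis, section 4.3 and section 7.1 to one structure: classes nested within schools.
- State the record unit for each analysis.
- Estimate the ICCs from the data instead of fixing 0.09. Report the school ICC with the caveat that eight schools make it very imprecise, and do not use it as a fixed correction.
- Judge size, area incidence and socio-economic level against between-school variation with a small-sample reference, and label the results descriptive. Examples are t on 8 − 2 = 6 df (2.45) for a single four-v-four contrast, or 8 − 4 = 4 df (2.78) if all three factors are fitted jointly. Only the 6 df version was checked by simulation.
- For overall rates, either allow for school-level variation in the same way or state that inference is limited to the eight purposively chosen schools.

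The cost is SAP wording and model specification, with no new data. Intervals that use the t reference widen by 25% at 6 df (2.447/1.96) or 42% at 4 df (2.776/1.96) from that reference alone, before any between-school variance is added.
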